9.3.2. Loss of TMA Response

For participants who meet the criteria for complete TMA response during the 26-week randomized Treatment Period, loss of TMA response is defined as when the participant fails to meet the criteria for 1 or more components of TMA response at a subsequent visit during the 26-week randomized Treatment Period. At least 1 parameter must fail to meet the response criteria at 2 separate assessments obtained at least 24 hours apart and any measurement in between. The first laboratory value will be assessed based on central laboratory results; the second laboratory value will be assessed based on the earliest value obtained \geq 24 hours after the first value and may be based on central or local laboratory results.

9.3.3. PLASMIC Score

The PLASMIC score is the sum of points from each qualifying component. The score will be used to stratify participants into low (0 to 4), intermediate (5), and high (6 to 7) risk categories for TTP (Table 3).

Table 3:PLASMIC Score Derivation

Components	Point
Platelet count $< 30 \times 10^9/L$	1
Hemolysis: Reticulocyte count > 2.5%, haptoglobin undetectable, or indirect bilirubin > 2.0 mg/dL (34.2 μ mol/L)	1
No active cancer: Not treated for cancer within the past year	1
No history of solid-organ or stem-cell transplant	1
$MCV < 9.0 \times 10^{-14} L (< 90 fL)$	1
INR < 1.5	1
Creatinine < 2.0 mg/dL (176.8 µmol/L)	1

Abbreviations: INR = international normalized ratio; MCV = mean corpuscular volume

9.3.4. Change from Baseline

Change in values from Baseline will be calculated as follows:

Change in value = (subsequent value – baseline value), given that both the baseline value and subsequent value are nonmissing.

9.3.5. Percent Change from Baseline

Percent change in values from Baseline will be calculated as follows:

Percent change in value = (change in value / baseline value) \times 100

where change in value = (subsequent value – baseline value), given that the baseline value is nonmissing and nonzero and the subsequent value is nonmissing.

9.3.6. Analysis Visits

Summaries over post-Baseline time points or analyses at specific post-Baseline time points will be performed based on the list of visits described in the SoA of the protocol. For all assessments in the 26-week randomized Treatment Period, the number of days from baseline will be calculated using the following formula: (date of assessment) - (date of Day 1 visit) + 1. This number of days will be used to assign analysis visit.

The analysis visit assignment for a specific assessment will be based on visit windows around each scheduled visit for that specific assessment. The windows for each scheduled visit will go from the midpoint (in days) between the current visit and the previous scheduled visit to the midpoint between the current visit and the subsequent scheduled visit. If the interval separating 2 scheduled visits is an even number of days, that middle day will be included in the later visit window and excluded from the prior visit window. For example, for an assessment with a scheduled visit on Day 71, a prior scheduled visit on Day 57, and a subsequent scheduled visit on Day 85, the window will start at 64 days from Baseline and will go to 77 days from Baseline.

9.3.7. Analysis Values

The values being considered for analysis at a specific post-Baseline time point will be based on the analysis visit assigned to that value. If there is more than 1 nonmissing value for a specific assessment with the same analysis visit, the value used for analysis will be the one for which the calculated number of days from baseline is closest to the scheduled visit day. If 2 values have the same analysis visit and are the at same distance away from the scheduled visit day, the earlier of the 2 values will be used for analysis.

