### **8.3.5. Clinical Safety Laboratory Assessments**

- All protocol-required laboratory assessments, as outlined in Section 10.2, must be conducted in accordance with the Laboratory Manual and the Schedule of Activities (Section 1.3).
- The Investigator must review the laboratory report, document this review, and record any clinically relevant changes occurring during the study in the AE section of the CRF. The laboratory reports must be filed with the source documents. Clinically significant abnormal laboratory findings are those which are not associated with the underlying disease, unless judged by the Investigator to be more severe than expected for the participant's condition.
- All laboratory tests with values considered clinically significantly abnormal during participation in the study should be repeated until the values return to normal or baseline or are no longer considered clinically significant by the Investigator.

Note: For participants that withdraw from the study, all laboratory tests with values considered clinically significantly abnormal within 8 weeks after the last dose of study drug should be repeated until the values return to normal or baseline or are no longer considered clinically significant by the Investigator.

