### 10.3. Clinical Laboratory Tests

- The tests detailed in Table 9 will be performed by the central laboratory or designated ancillary laboratories unless otherwise noted.
- As described in Section 5, local or central laboratory results may be utilized for the assessment of eligibility, with the exceptions of the ST-HUS screen and ADAMTS13 activity tests which must be performed at the central laboratory. With the exceptions of the ST-HUS screen and ADAMTS13 activity tests, if local labs are used to establish eligibility, central laboratory tests are not required at the Screening visit.
  - For participants who experience constipation and cannot produce a stool sample for the ST-HUS screen during the Screening period, an assessment of the presence of Shiga toxin-producing *E. coli* infection can be evaluated by the Investigator based on the clinical presentation of the participant. If a stool sample for the ST-HUS screen cannot be obtained during the Screening period, laboratory evaluation for the ST-HUS screen will be made from the first available stool sample, which may include samples obtained post randomization.
  - After the Screening Period, local laboratory results are only required in the event the central laboratory results are not available in time for either study drug administration and/or response evaluation. Additionally, if the local laboratory results are used to make either a study intervention decision or response evaluation, the results must be entered into the CRF. If a local sample is obtained, it is important that the sample for central analysis is obtained at the same time.
- Protocol-specific requirements for inclusion or exclusion of participants are detailed in Section 5 of the protocol.
- Additional tests may be performed at any time during the study as determined necessary by the Investigator or required by local regulations.
- Pregnancy testing: WOCBP should only be enrolled after a negative serum pregnancy test result at Screening (serum pregnancy test to be collected at Screening, Day 183, and EOS/ED). Urine pregnancy testing will be performed at all other timepoints as

specified in the Schedule of Activities (Section 1.3) unless serum testing is required by site policies, local regulation, or IRB/IEC.

- Investigators must document their review of each laboratory safety report.

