7.7.3. Other Safety

7.7.3.1. Analyses for Laboratory Tests

Observed values and changes from Baseline in clinical chemistry, hematology, and urinalysis will be summarized descriptively by treatment group at Baseline and at each post-Baseline time point. For laboratory results that can be classified as normal, low, or high based on normal range values, shifts from baseline in classification will be summarized by treatment group for all study visits. For purposes of analyses, laboratory results based on standardized units will be used.

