7.7.3.3. Electrocardiograms

ECGs will be evaluated and summarized as normal, abnormal not clinically significant, or abnormal clinically significant. A shift from baseline to worst on-study ECG table will be presented by treatment group for ECG results. Observed values and change from Baseline in ECG intervals (PR, RR, QT, and QTc) will be summarized descriptively by treatment group at Baseline and each post-Baseline time point. QT interval will be corrected using QTcF.

A listing of ECG results will also be presented by treatment group, participant, and visit.

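### The laboratory shift tables use only the value nearest each scheduled visit day, so they can miss a worse laboratory value in the same window; the consequence here is minor

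*SAP*

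**What the plan says.** SAP 9.3.6 sets the scope: "Summaries over post-Baseline time points or analyses at specific post-Baseline time points will be performed based on the list of visits" in the protocol schedule. Each assessment is assigned to a scheduled visit by a window running to the midpoints between neighbouring visits. SAP 9.3.7 then reduces each window to one value per parameter, namely "the one for which the calculated number of days from baseline is closest to the scheduled visit day". If two values are equally far from that day, "the earlier of the 2 values will be used for analysis". Neither section separates efficacy from safety data.

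For laboratory tests, SAP 7.7.3.1 plans descriptive summaries at each time point, and "shifts from baseline in classification will be summarized by treatment group for all study visits". Protocol 9.4.2.3 has the same by-visit shift table. No table of the worst post-Baseline laboratory value is planned. For vital signs, SAP 7.7.3.2 plans by-visit summaries and a listing, with no shift table. For ECGs, SAP 7.7.3.3 differs: "A shift from baseline to worst on-study ECG table will be presented by treatment group for ECG results".

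The protocol makes several laboratory values per window likely. Under 8.3.5, clinically significant abnormal tests "should be repeated until the values return to normal or baseline", or until the Investigator no longer regards them as significant. Under 10.3, "Additional tests may be performed at any time during the study as determined necessary by the Investigator".

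**The concern.** A laboratory shift table should show who moved from an acceptable Baseline to an abnormal result on study. In this acutely ill population, some of the most abnormal results may come from samples taken between visits. Such a sample falls into a neighbouring visit's window and competes with the scheduled draw. If the scheduled draw is nearer the nominal day and normal, the table records normal for that visit.

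Adverse event tables recover only part of this. Protocol 8.3.5 has the Investigator record clinically relevant laboratory changes as adverse events. However, 8.3.5 and 10.4.1 leave out abnormalities attributed to the underlying disease unless they are worse than expected for that participant. In TMA, falls in platelets or hemoglobin and rises in LDH or creatinine can be attributed to the disease. A real deterioration in these could then appear in neither the adverse event tables nor the shift tables, and be visible only in a listing.

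**Working it through.** **Inputs.** Laboratory visit days from protocol Tables 1 and 2: 1, 8, 15, 22, 29, 43, 57, 71, 85, 99, 127, 155, 183, then 365. Window rule from SAP 9.3.6, with a middle day going to the later visit. Selection and tie rules from SAP 9.3.7.

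**Formula.** Lower limit = (previous + current)/2, rounded up. Upper limit = (current + next)/2, rounded up, minus 1.

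**1. The SAP's own example.** For Day 71, between Days 57 and 85: lower = (57 + 71)/2 = 64; upper = (71 + 85)/2 − 1 = 77. This matches the Day 64 to 77 window in SAP 9.3.6.

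**2. Other laboratory windows.**
- Day 8: (1 + 8)/2 = 4.5, rounded up to 5; (8 + 15)/2 = 11.5, rounded up to 12, minus 1 = 11. Days 5 to 11, 7 days.
- Day 127: (99 + 127)/2 = 113; (127 + 155)/2 − 1 = 140. Days 113 to 140, 28 days.
- Day 155: (127 + 155)/2 = 141; (155 + 183)/2 − 1 = 168. Days 141 to 168, 28 days.

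**3. Days on which another value can displace the scheduled draw at the Day 155 visit.** The visit allows ±3 days. A value on day d displaces a draw on day s if d is nearer to 155 than s, or equally near and earlier.
- s = 155: no other day.
- s = 158: Days 152 to 157, 6 of 28 days (Day 152 wins the tie).
- s = 152: Days 153 to 157, 5 of 28 days (Day 158 loses the tie).

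**4. Hypothetical sequences.** The documents give no count of unscheduled values, so these only show how the rule behaves.

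| Values | By-visit and shift table | Worst post-Baseline value |
|---|---|---|
| Day 71 normal, Day 75 high | Normal | High |
| Day 71 normal, Day 79 high, Day 85 normal | Normal at both visits (Day 79 is in the Day 85 window, 78 to 91) | High |
| Day 68 high, repeat on Day 71 normal | Normal | High |
| Day 71 high, repeat on Day 74 normal | High | High |
| Day 74 high, repeat on Day 77 normal | High | High |
| Day 71 missed, Day 75 high | High | High |

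The first three rows show the gap. The last three show that an abnormal value survives when it is closest or alone.

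**5. After Week 26.** SAP 9.3.6 states its day count for the Treatment Period. If the midpoint rule is carried further (an assumption), the Day 183 laboratory window runs from 169 to (183 + 365)/2 − 1 = 273, because the next scheduled laboratory visit is Day 365. A high value on Day 230 would then lose to a normal value on Day 183.

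**6. Weight of one participant.** With 16 enrolled and 1:1 allocation, about 8 per arm is assumed. One participant then moves a shift percentage by 1/8 = 12.5 points.

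**The case against.** A reader might infer that unselected values are thrown away. The documents do not support that: SAP 7.7 provides for listings of all safety data, so these values are missing from summaries, not from the report. With 16 participants, the listings can be read individually.

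A reader might also infer that unscheduled results always lose to scheduled ones. Selection is by distance from the nominal day, so an unscheduled abnormal value is used when it is closest or the only one. Mandatory repeats are weaker support than they look. They follow an abnormal result, and an abnormal draw on the scheduled day outranks every later repeat. A repeat replaces it only in narrower cases, such as Day 68 high and Day 71 normal.

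Nor does the shift-table point extend to vital signs, since none is planned for them.

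The ECG comparison can be questioned too. ECGs have one scheduled post-Baseline time point (Day 183 or early discontinuation), whereas laboratory tests have 12 scheduled treatment visits after Day 1. By-visit laboratory shifts are the protocol's own plan, and the early windows are only about 7 days long. Because entry required low platelets, raised LDH and hemoglobin no higher than the lower limit of normal, a worst-value shift for those three would often run from abnormal to abnormal.

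All of this limits the consequence. It leaves one fact standing: an abnormal laboratory value can be absent from every laboratory summary table, and for disease-related findings the adverse event tables need not supply it. More frequent visits shorten the windows but do not change how one value is chosen within each.

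**Conclusion.** The point holds for laboratory data and is minor. SAP 9.3.7 has no safety exception, and the laboratory shift tables are by visit only, so they can miss a participant's worst post-Baseline value. The omission is conditional on another value in the same window lying nearer the scheduled day, or equally near and earlier.

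Its frequency cannot be estimated from the documents. The 5-or-6-of-28-day figure describes the longest Treatment Period windows with a draw 3 days off; it is not a rate of missed abnormalities. The SAP plans no inferential comparison of the arms, and the study closed enrollment at 16. Nothing here supports a claim that safety data are lost or that a treatment comparison is biased. The case for change is that descriptive tables are the main output, the better rule costs little, and the SAP already uses it for ECGs.

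**What to change.** State in SAP 9.3.7 that the closest-value rule applies to efficacy and by-visit summaries. Add to 7.7.3.1 a shift from Baseline to worst post-Baseline laboratory value, separately for the Treatment and Follow-up Periods. Use all scheduled, unscheduled, early-discontinuation and CRF-recorded local results, with central results prevailing for duplicate samples as in SAP 5.5.3. Keep the by-visit tables beside it.

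Two details need a sentence each: the direction of worst for each parameter, and whether the exclusions around dialysis and transfusion (SAP 9.3.10 and 9.3.11) apply to this table. For vital signs there is no shift table to correct; a summary of extreme values is optional.

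The cost is SAP wording and a few tables from data already held. There are two limits. Participants who are sampled more often have more chances of an extreme value, so worst values depend partly on sampling frequency. Also, protocol 10.3 requires local results in the CRF only when they inform a study-intervention decision or response evaluation, so some local results may not be available.

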9.3.8. Adverse Events

TEAEs are events with start dates on or after the date of the start of the first infusion of study drug and up to 8 months after the last infusion of study drug. If the start date of an AE is partially or completely missing and the end (stop) date of the AE does not indicate that it occurred prior to first dose or 8 months after last dose, then the determination of treatment-emergent status will be based on the following:

- If the start year is after the year of the start of first infusion of study drug and before the year of last infusion of study drug, then the AE is treatment emergent.
- If the start year is the same as the year of the start of the first infusion of study drug and
 - The start month is missing, then the AE is treatment emergent

OR

- The start month is present and is the same or after the month of the first infusion of study drug, then the AE is treatment emergent
- If the start date is completely missing, then the AE is treatment emergent.

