**Table 7: Weight-based Doses of Ravulizumab**

Body Weight Range a	Loading Dose (Day 1)	Maintenance Doses (Days 15, 71, and 127)
≥ 30 to < 40 kg	1200 mg	2700 mg
≥ 40 to < 60 kg	2400 mg	3000 mg
≥ 60 to < 100 kg	2700 mg	3300 mg
≥ 100 kg	3000 mg	3600 mg

a Dose will be based on the last recorded study visit body weight. If the study drug is prepared the day before a visit, the weight from the most recent study visit should be used.

At the scheduled dosing visits (Section 1.3), study drug should be administered after all other tests and procedures have been completed, excluding the postdose sample collections (pharmacokinetic [PK]/pharmacodynamic [PD]/biomarkers).

During the Treatment Period, participants will be randomized 1:1 to receive blinded doses of ravulizumab or placebo:

- Participants in the ravulizumab group will receive a blinded loading dose of ravulizumab via IV infusion on Day 1, followed by a blinded maintenance dose at Day 15 then q8w thereafter through the end of the Treatment Period.
- Participants in the placebo group will receive a blinded matching placebo dose via IV infusion on Day 1, followed by a blinded matching placebo dose at Day 15, then q8w thereafter through the end of the Treatment Period.

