### **8.4.1. Time Period and Frequency for Collecting AE and SAE Information**

All AEs and SAEs will be collected from the signing of the ICF until the EOS Visit. For participants who withdraw from the study during the Treatment Period, all AEs and SAEs should be collected through 8 weeks after last dose of study drug. For participants who discontinue study drug, but remain in the Follow-up Period, all AEs and SAEs will be collected through the EOS Visit.

All SAEs will be recorded and reported to Alexion or the designee immediately and under no circumstance should this exceed 24 hours, as indicated in Section 10.4. The Investigator, or designee, will submit any updated SAE data to Alexion within 24 hours of the date the study site became aware of the event.

Investigators are not obligated to actively seek AE or SAE data after conclusion of the study participation. However, if the Investigator learns of any SAE, including a death, at any time after a participant has concluded participation in the study, and he/she considers the event to be

reasonably related to the study drug or study participation, the Investigator must promptly notify Alexion.

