7.7. Safety Analyses

All safety analyses will be conducted on the Safety Set and based on the actual treatment received. All safety data will be provided by treatment group, in participant listings. AEs will be coded in MedDRA and presented by MedDRA SOC and Preferred Term. No formal hypothesis testing is planned. Safety data will be presented separately for the 26-week randomized Treatment Period and Post-Treatment Follow-up Period.

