7.7.2. Adverse Events

The following definitions will be used for AEs:

- Pretreatment AEs: Any AE that starts after providing informed consent/assent, but before randomization or before the start of the first infusion of study drug.
- Treatment-emergent adverse event (TEAE): Any AE that starts between the first infusion of study drug and up to 8 months after the last infusion of study drug.
- Treatment-emergent serious adverse event (TESAE): A TEAE that is serious.

The incidence of TEAEs, TEAEs leading to withdrawal from the study, TEAEs leading to study treatment discontinuation, drug-related TEAEs, TEAEs during study drug administration, and SAEs will be summarized by treatment group. All AEs will be coded using MedDRA version 23 or higher and will be summarized by SOC and Preferred Term overall, severity, and relationship to treatment. Participants having multiple AEs within a category (eg, overall, SOC, Preferred Term) will be counted once in that category. For severity/relationship tables, the participant's highest grade/most related event within a category will be counted. Percentages will be based on the number of treated participants in the Safety Set within a treatment group and overall. Tables will be sorted by descending frequency of SOC and by descending frequency of Preferred Term within an SOC.

Detailed by-participant listings of pretreatment AEs, TEAEs, SAEs, related TEAEs, TEAEs during study drug administration, TEAEs leading to withdrawal from the study, and TEAEs leading to study treatment discontinuation will be provided.

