7.7.2.1. Overall Summary of Adverse Events

An overall summary of AEs and SAEs will be presented. The number of events (n) and number of participants with events (n, %) will be shown for the following event subcategories:

- Any TEAE
- Any TESAE
- TEAEs leading to withdrawal from the study
- TEAEs leading to study treatment discontinuation
- Study drug-related TEAEs
- TEAEs during study drug administration

Additionally, the number and percentage of participants who died during the study will be presented. AEs and SAEs by SOC and Preferred Term. The number of AEs and the number and

percentage of participants with events will be presented by SOC and Preferred Term. Participants are counted once in each SOC and Preferred Term. Percentages will be based on the total number of treated participants in the treatment group. SAEs will be summarized similarly.

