7.7.2.3. AEs by SOC, Preferred Term, and Severity

The number of AEs and the number and percentage of participants with events will be presented by SOC and Preferred Term as described above by severity (Grade 1, Grade 2, Grade 3, Grade 4, Grade 5). If a participant has more than 1 occurrence of an AE, the most severe occurrence will be used in the summary table.

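### The first partial-date rule for treatment-emergent AEs in SAP 9.3.8 can never apply, so an AE dated to a later calendar year falls under no rule

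*SAP*

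**What the plan says.** SAP 7.7.2 defines a TEAE as "Any AE that starts between the first infusion of study drug and up to 8 months after the last infusion of study drug", and SAP 9.3.8 opens with the same window. For an AE whose start date is partly or wholly missing, and whose stop date does not rule it out, 9.3.8 says "then the determination of treatment-emergent status will be based on the following". Three bullets follow:

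1. The first has the condition "If the start year is after the year of the start of first infusion of study drug and before the year of last infusion".
2. The second applies when the start year equals the first-infusion year. The AE is flagged if the month is missing, or is the first-infusion month or later.
3. The third flags an AE with no start date at all.

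There is no bullet for any other later year and no default.

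The parallel rule for medications in SAP 9.3.9 differs on both counts. Its later-year bullet has no upper year bound, and it ends by classing everything left over as prior.

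**The concern.** The first bullet is the only one that deals with a start year after the first-infusion year. If it cannot be met, a known later year with a missing day or month is sent to a list that has no entry for it. The text does not call such an AE non-treatment-emergent, but a program written from it would set no flag. The result is perverse: an AE with no date at all is flagged, while one known to have begun during dosing in the second calendar year is not.

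The second bullet has the reverse weakness. It never checks the 8-month limit. Protocol 8.4.1 states: "For participants who discontinue study drug, but remain in the Follow-up Period, all AEs and SAEs will be collected through the EOS Visit". Events past the limit can therefore be recorded for someone who stops early, and a partial date in the first-infusion year would be flagged regardless.

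What is at stake is the output restricted to TEAEs: the TEAE listings in SAP 7.7.2 and the overall summary in SAP 7.7.2.1, where "The number of events (n) and number of participants with events (n, %) will be shown for the following event subcategories".

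**Working it through.** **Inputs.** Infusions on Days 1, 15, 71 and 127 (Protocol Table 7); visit window of ± 3 days at Day 127 and end of treatment at Day 183 (Protocol Table 1); Week 52 visit at Day 365 (Protocol Table 2); TEAE limit 8 months after the last infusion (SAP 7.7.2 and 9.3.8). The plan gives no figure of its own to reproduce.

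**Step 1: can the first bullet be met?** It needs first-infusion year < start year < last-infusion year, so the two infusion years must differ by at least 2. The shortest such span runs from 31 December to 1 January two calendar years on, for example 31 Dec 2021 to 1 Jan 2023, which is 366 days. The last infusion comes at most 130 − 1 = 129 days after the first. The largest possible difference is therefore 1. Testing every Day 1 date from 17 Dec 2020 to 31 Dec 2024 (an assumed range) gave 0 of 1476 dates that satisfy the bullet, even with the last infusion placed at Day 365.

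**Step 2: what is left uncovered?**

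| Known part of start date | Bullet that applies |
|---|---|
| Nothing | Third: flagged |
| First-infusion year, month missing or not earlier than first-infusion month | Second: flagged |
| Later year, month missing | None |
| Later year and month, day missing | None |

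**Step 3: two examples.**

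- *Day missing.* Doses on 15 Oct, 29 Oct and 24 Dec 2021 and 18 Feb 2022; AE dated Jan 2022. Every day of that month lies between the third and fourth infusions, so it is a TEAE by definition. No bullet flags it.
- *Month missing.* First infusion 1 Jun 2022, last 5 Oct 2022; AE dated only 2023. The limit is 5 Jun 2023 and Day 365 is 31 May 2023, so any 2023 onset up to Day 365 is inside the window. No bullet flags it.

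**Step 4: how often does the calendar allow this?** All 365 start dates are counted equally. These are shares of start dates or days, not of AEs.

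- Day 127 falls in the next year for the last 126 start dates of the year: 126/365 = 34.5% (123 dates at Day 124, 129 at Day 130).
- Day 183 does so for 182/365 = 49.9%.
- Second-year share of Days 1 to 183: (1 + 2 + … + 182)/(365 × 183) = (182 × 183/2)/(365 × 183) = 91/365 = 24.9%.
- All of January ends on or before Day 127 when Day 1 is no earlier than 31 January minus 126 days, which is 27 September. That gives 4 + 31 + 30 + 31 = 96 dates, 96/365 = 26.3%.

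**Step 5: the opposite error.** A first-year month lies wholly past the limit if the last dose plus 8 months is 30 November or earlier, so that December is outside. The last dose must then be on or before 31 March.

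| Last dose received | Latest Day 1 | Start dates | Share of 365 |
|---|---|---|---|
| Day 1 | 31 Mar | 90 | 24.7% |
| Day 15 | 17 Mar | 76 | 20.8% |
| Day 71 | 20 Jan | 20 | 5.5% |
| Day 127 | none | 0 | 0% |

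Example: a single dose on 5 Jan 2022 gives a limit of 5 Sep 2022, while Day 365 is 4 Jan 2023. An ongoing AE dated Nov 2022 is wholly outside the window. It has no stop date to exclude it, and the second bullet flags it.

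**The case against.** The best reply is that the general definition already settles many of these cases. When only the day is missing, the month and year often place the event clearly inside or outside the window, as with the January and November examples. A sensible programmer would apply the definition. That is fair, and it makes the day-missing case a conflict between the definition and the bullets. It does not remove the conflict, because the lead-in sends all partial dates to the bullets. With the month missing the gap is plainer still.

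A second reply concerns layout. The sub-bullet that compares months is read here as part of the second bullet. If it stood alone, and month meant month and year together, the January example would be covered. The indentation is not visible in the text available, but the matching list in SAP 9.3.9 supports the nested reading. The month-missing gap remains on either reading.

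A third reply is about weight, and it stands. No passage says how many AEs have partial dates, so the percentages above measure the calendar and not the impact. The opposite error needs early discontinuation, continued follow-up and a partial date in the first-infusion year. Its effect is limited further because SAP 7.7 presents the Treatment and Follow-up Periods separately.

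**Conclusion.** The rule is wrong as written, and the error is minor. The first bullet is empty under this dosing schedule. Later-year partial dates have no rule and no default, and the second bullet ignores the SAP's own 8-month limit. The conclusion assumes infusions within the scheduled windows and the nested reading of the month sub-bullet.

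The practical effect is small: 16 participants were enrolled, no hypothesis testing is planned (SAP 4.2), and no efficacy result is touched. An unflagged event would not vanish. SAP 7.7 promises that "All safety data will be provided by treatment group, in participant listings", and tables worded as AEs, such as the one in SAP 7.7.2.3 ("The number of AEs and the number and percentage of participants with events will be presented by SOC and Preferred Term"), would still show it. Only counts and listings restricted to TEAEs are exposed, and the number of events concerned may be zero.

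**What to change.** Replace the three bullets and their lead-in with one sentence:

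> An AE with a partially or completely missing start date is treatment-emergent unless the known part of its start date shows that it began before the first infusion or more than 8 months after the last infusion, or its stop date is before the first infusion.

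This closes the later-year gap, applies the 8-month limit to every case, and keeps the present leaning towards inclusion when the date is uninformative. It drops the stop-date check against the 8-month limit, but nothing is lost: a late stop date does not show a late onset.

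Removing only the upper year bound, as in SAP 9.3.9, would cover later years but leave the limit unchecked.

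The cost is one sentence in the SAP and a small change to the derivation. TEAE counts may rise slightly, or fall for a participant who stopped early.
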